#### **4.2 Exclusion Criteria:**

1. Patient with active heart disease (NYHA class  $\geq$  3 as assessed by history and physical examination).
2. Patients with a cardiac ejection fraction (as measured by either MUGA or echocardiogram)  $<$  45% are excluded.
3. Patients who receive other chemotherapy. Patients must have been off previous therapy for  $\geq$  2 weeks and must have recovered from acute toxicity (to grade 1 or less) of all previous therapy prior to enrollment (consent signing). (Concurrent therapy for central nervous system [CNS] prophylaxis or treatment for CNS relapse is permitted). Treatment may start earlier if

necessitated by the patient's medical condition (e.g. rapidly progressive disease) following discussion with the Principal Investigator.

4. Prior allogeneic stem cell transplant in previous 4 months.
5. Peripheral lymphoblasts  $> 50 \times 10^9/L$ .
6. Pregnant and breast-feeding patients are excluded.
7. Patients with known hepatitis B are excluded.

## **5.0 Treatment Plan**

### **5.1 General**

This is an open label, phase II study. The design will evaluate single agent efficacy of CMC-544 as initial treatment, first in patients  $\geq 16$  years and then in patients less than 16 years. If stable disease or worse after 2 courses, CMC-544 will continue with the addition of rituximab, as detailed below.

CMC-544 will be provided by Wyeth Corporation. Any unused or expired drug will be destroyed per institutional policy.

### **5.2 Treatment Schema**

**5.2.1** The first 3 patients  $\geq 16$  years and the first 3 patients  $< 16$  years will receive CMC-544 at a dose of  $1.3 \text{ mg/m}^2$  IV over 1 hour (+/- 15 minutes) during Course 1, and  $1.8 \text{ mg/m}^2$  IV over 1 hour (+/- 15 minutes) during Course 2 and subsequently. In all other patients, if there are no safety issues, CMC-544 will be given at a dose of  $1.8 \text{ mg/m}^2$  IV over 1 hour (+/- 15 minutes) about every 4 weeks. This will constitute a course of therapy. Courses will be repeated about every 4 weeks (range 3-6 weeks).

Courses can be started earlier, every 2 weeks if evidence of rapid progression after approval by the principal investigator.

**5.2.2** In a second phase (see 2.4), 20 patients will be treated with weekly CMC-544. CMC-544 will be given at 0.8 mg/m^2 IV over 1 hour ( $\pm$  15 minutes) on Day 1, 0.5 mg/m^2 IV over 1 hour ( $\pm$  15 minutes) on Day 8, and 0.5 mg/m^2 IV over 1 hour ( $\pm$  15 minutes) on Day 15. Weekly doses can be given at  $\pm$  1 day. Course may be repeated every 3 weeks.

Recommended premedication before CMC-544: acetaminophen 650 mg orally, diphenhydramine 10-25 mg IV, hydrocortisone 25 mg IV. Modifications to this premedication are also allowed.

Prophylaxis for tumor lysis syndrome may be administered at the discretion of the treating physician.

**5.2.3** If stable disease, no improvement or progression after 2 courses of CMC-544, patients may continue on CMC-544 at the same dose every 3-4 weeks, with the addition of rituximab 375 mg/m^2 IV over 2-6 hours every 3-4 weeks. The first dose of rituximab will be given as a slow infusion over 6-8 hours depending on reactions and side effects. It will be given on Day 1 and CMC-544 on Day 2. Subsequent courses of CMC-544 and rituximab may be given on the same day; CMC-544 will be given at least 2-4 hours after completion of rituximab. Courses can be started earlier, every 2 weeks if evidence of

rapid progression after approval by the principal investigator. In the second phase of weekly CMC-544, rituximab will be given on Day 1 and CMC-544 on Day 2 of the first dose; with subsequent weekly doses, both will be given weekly, rituximab preceding CMC-544. The weekly dose of rituximab will be 375 mg/m^2.

Infusion 1 of rituximab will be over 6-8 hours following infusion rate increases as per hospital standards. Infusions 2-6 of rituximab may be run at faster rates of 2-6 hours as indicated by side effects and per hospital standards.

**5.2.4** Patients achieving response, defined as CR or CRi, or partial remission (PR) may continue therapy for up to 8 cycles (about 8-12 months of therapy). Patients with progression at any time or without objective response after 3 cycles will be taken off study.

### **5.3 Treatment Duration and Dose Adjustments**

Patients will receive 2 courses of CMC-544. If CR, complete remission without platelet recovery (CRi), or PR is documented, whichever comes first, then continue CMC-544. If a patient does not achieve a CR, CRi, or PR then add rituximab as under 5.2.

Patients who achieve a CR, CRi, or PR may receive up to a total of 8 cycles of therapy depending on leukemia response and resolution of toxicities. Subjects who demonstrate a CR or CRi after 1 or 2 cycles of therapy will receive a maximum of 4 cycles of therapy. Subjects who are in a CR or CRi after 3-4 cycles may receive a maximum of 2

additional cycles of therapy after achieving a CR or CRI. After a total of 4 cycles, patients will be assessed for the need of the 4 additional cycles based on response and liver toxicities with the previous 4 cycles. Cycles are repeated about every 4 weeks (range 3-6 weeks) depending on leukemia response, resolution of toxicities, and recovery of hematopoiesis.

Patients receiving subsequent cycles (cycles 2-8) will be treated at the same dose level if grade  $\leq$  2 non-hematologic toxicity has occurred and if they have experienced a favorable response of their leukemia (decrease in peripheral blood or marrow blasts). Re-treatment will only occur upon recovery to < grade 2 non-hematologic or baseline toxicity. If they have non-hematologic toxicity of  $\geq$  grade 3 and a favorable response to therapy, additional cycles of therapy at 25% dose reduction of CMC-544 may be considered after this is discussed with and approved by the Principal Investigator. No dose reductions for rituximab are needed.

Patients who develop CNS leukemia while on study will be removed from the study and receive CNS-directed therapy, except where such patients have a positive response to therapy in which case they will continue on study after discussion with the Principal Investigator.

#### **5.4 Concomitant Medications**

Necessary supportive measures for optimal medical care will be given throughout the study as determined by the treating physician and the patient's medical need. No

concomitant chemotherapy (with the exception of prophylactic or therapeutic intrathecal chemotherapy for active CNS disease or CNS disease in remission), immunotherapy, or therapy with monoclonal antibodies will be allowed during the study. Investigational agents that are not used for the treatment of the leukemia per se (e.g. anti-infective prophylaxis or therapy) will be allowed.

Use of any hematopoietic growth factor (e.g. G-CSF, GM-CSF, or erythropoietin) is at the discretion of the treating physician and is permitted if judged in the patient's best medical interest.

Prophylactic antibiotics, antifungals, and antiviral agents (e.g. levofloxacin, itraconazole, valacyclovir, etc.) are recommended; however, the use of these or other drugs will be left to the treating physician's discretion.

The use of hydroxyurea or steroids is permitted for temporary control of WBC elevations in patients with aggressive disease both prior and during treatment. Hydroxyurea may be given at 1-5 g daily for up to 5 days in Course 1. Dexamethasone may be given at 40 mg daily x 4 with each of the first 2 courses.

## 6.0 Pretreatment evaluation

Procedure	Comments	Schedule
Informed Consent	Obtain standard informed consent approved by IRB	Within 14 days of study start

Procedure	Comments	Schedule
Medical History	Includes history of present illness, prior cancer history as far as traceable, and past medical/surgical history as far as relevant.	Within 14 days of study start
Physical Examination	Includes vital signs (temperature, heart rate, respiratory rate, blood pressure) and performance status	Within 14 days of study start
Concomitant Medications	Document concomitant medications as far as traceable.	Within 14 days of study start
Hematology	CBC with differential and platelet count	Within 14 days of study start
Biochemistry	Creatinine, bilirubin, SGPT or SGOT, uric acid	Within 14 days of study start
Pregnancy test	Serum or urine	Within 14 days of study start
Bone Marrow	Aspirate and/or biopsy. Flow cytometry if required to establish diagnosis.	Within 30 days of study start
MUGA or Echocardiogram	Assessment of QTc and cardiac ejection fraction	Within 30 days of study start
Immunophenotype	Assess ALL markers including CD22	Within 14 days of study start
Flow cytometry	CD22 expression	Within 14 days of study start
Optional: In vitro CMC-544 sensitivity studies (Pharmacokinetics)	CMC-544 saturation and survival studies	Within 14 days of study start

## 7.0 Evaluation during therapy

Procedure	Comments	Schedule
Physical Examination	Includes recording of vital signs, concomitant medications, adverse events, and performance status	Prior to each subsequent course.
Hematology	CBC with differential (if granulocytes > $1.0 \times 10^9/L$ ) and platelet count	1 to 3 times weekly during induction (courses 1 and/or 2) i.e. until achievement of response, then at least weekly during consolidation.

Procedure	Comments	Schedule
Biochemistry	Creatinine, bilirubin, SGPT or SGOT.	Weekly during induction (courses 1 and/or 2), then at least once every 2 weeks during consolidation.
Bone Marrow	Aspirate and/or biopsy.	Bone marrow at Day 14-21(+/- 3 days), then as indicated in course 1 to confirm response, and then every 1-2 courses to confirm response. Other marrow examinations as indicated. No bone marrow is necessary if non-response or progressive disease can be diagnosed from peripheral blood evaluation, or, in patients with a WBC < 0.3, if the bone marrow test is considered non-contributory by the Investigator. Cytogenetic studies only if abnormal prior to study and/or the additional information is considered of consequence. Cytogenetic studies may be assessed on any bone marrow at the discretion of the treating physician. Further bone marrow tests as indicated by development of peripheral blood counts.
ECGs	Assessment of QTc and cardiac ejection fraction	Patients with history of arrhythmias or angina will have ECGs performed prior to the start of the rituximab, once during the infusion, and within 2 hours post infusion. Rituximab infusion will be discontinued for any clinically significant cardiac arrhythmia. In addition, all patients should have 12-lead ECG assessments to evaluate the potential for QTc prolongation regarding CMC-544 therapy. ECGs should be collected prior to course 1 CMC-544.
Diagnostic evaluation		Patients with complaints of abdominal pain will be examined for any signs or symptoms of bowel obstruction and/or perforation. Appropriate radiologic tests and surgical consults will be performed as needed.
CD22 expression	If peripheral blast count > 5000	CD22 expression obtained pretreatment
Pharmacokinetics (CMC-544) (optional) (see the laboratory manual or processing instruction)	During Course 1	PK during course 1: Day 1 pre-dose, end of infusion, 3 hrs post, Day 8 pre-dose, end of infusion, 3 hrs post, and Day 15 pre-dose, end of infusion, 3 hrs post.

Patients are allowed to have hematology tests performed in outside laboratory facilities. Laboratory results will be obtained by the research nurse assigned to this study.

## **7.1 Post Treatment Evaluation**

Patients will be evaluated 30 days post receiving the last treatment of CMC-544 to collect information regarding toxicity unless the patient receives further therapy. This could be done during a regular clinic or inpatient visit or by phone call (research nurse or physician) if patient cannot be physically present at MD Anderson.

## **8.0 Criteria for Response**

**8.1 Complete remission (CR):** Disappearance of all clinical and/or radiologic evidence of disease. Neutrophil count  $\geq 1.0 \times 10^9 /L$ , platelet count  $\geq 100 \times 10^9 /L$ , and normal marrow differential ( $\leq 5\%$  blasts).

**8.2 Complete remission without recovery of counts (CRI):** Peripheral blood and marrow results as for CR, but with incomplete recover of counts (platelets  $< 100 \times 10^9 /L$ ; neutrophils  $< 1 \times 10^9 /L$ ).

**8.3 Partial remission (PR):** Peripheral blood count recovery as for CR, but with decrease in marrow blasts of  $\geq 50\%$  and not more than 25% abnormal cells in the marrow.

**8.4 Other:** All other responses will be considered as failures.

## **9.0 Criteria for Removal from the Study**

The Investigator may remove patients from the study for any of the following reasons:

**9.1 Progressive disease.** This is defined as a doubling of the peripheral blasts and an absolute increase of  $> 5 \times 10^9/L$ .

**9.2** Unacceptable adverse events/toxicities (any  $>/=$  grade 3 non-hematologic toxicity that does not at least resolve to < grade 2 or baseline).

**9.3** Investigator thinks a change of therapy would be in the best interest of the patient.

**9.4** If the patient has intercurrent, non-leukemia-related illness that would, in the judgment of the Investigator, affect assessments of clinical status to a significant degree and require discontinuation of protocol therapy.

**9.5** Patient request.

**9.6** Patient is non-compliant with protocol requirements.

The Principal Investigator has the right to terminate this study at any time. Reasons for terminating the study may include, but are not limited to:

**9.7** If the incidence or severity of adverse events indicates a potential health hazard to patients.

**9.8** If the patient enrollment is unsatisfactory.

## **10.0 Reporting Requirements**

Adverse event reporting will be as per the NCI criteria and the MDACC Leukemia Specific Adverse Event Recording and Reporting Guidelines.

The descriptions and grading scales found in the revised NCI Common Terminology Criteria for Adverse Events (CTCAE) version 3.0 (**Appendix A**) will be utilized for adverse event reporting. (<http://ctep.cancer.gov/reporting/ctc.html>).

Refer to **Appendix E** for Leukemia-Specific Adverse Event Recording and Reporting Guidelines. Only unexpected AEs will be recorded in the Case Report Form (CRF). The Principal Investigator will sign and date the PDMS Case Report Form toxicity pages per each patient at the completion of each course. Following signature, the Case Report Form will be used as source documentation for the adverse events for attribution.

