# **Treatment of Relapsed or Refractory Acute Lymphoblastic Leukemia (ALL) with CMC-544 (Inotuzumab Ozogamycin), with or without Later Addition of Rituximab**

## **1.0 Objectives**

- To evaluate the efficacy of treatment with CMC-544 with or without later rituximab in patients with relapsed or refractory ALL.
- To evaluate the side effects of the treatment.

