#### **2.4      Update of October 6, 2010**

At present, a total of 21 patients with refractory relapse ALL have been treated. Fifteen of them were in second salvage or worse; eight of them have translocation 4;11 or Philadelphia positive ALL. Overall, 12 of 21 patients have achieved either CR (n=5) or Cri (n=7), for an overall response rate of 57%. This is even better than what is expected using standard combination intensive chemotherapy in first salvage, with which the CR rate would be expected to be about 30%. Toxicity has been minimal. There were two episodes of tumor lysis responding to standard measures. Fever on Day 2 post therapy is common. Transient grade 1-3 elevations of liver enzymes have been observed, which are expected and self-limited. Two patients died within four weeks, one of them with progressive disease. Overall the treatment appears to be extremely effective with minimal toxicity. This has allowed so far at least 4 patients to undergo allogeneic stem cell transplant. Based on the findings we propose to 1) allow treatment of patients in first salvage regardless of the duration of first CR, and 2) increase the total number of

patients to 60 to allow more accurate assessment of the overall response rate and define more precisely predictive factors for response to therapy.

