## **2.5 Update of January 7, 2011**

At the present update, 38 patients have been treated. Of 32 evaluable patients, 8 achieved CR and 10 achieved CRI or CRp for an overall response rate of 18/32 =56%. Toxicities were reasonable and included Grade 1-2 elevations of liver function tests which were transient. Two patients had Grade 3 liver function abnormalities; the attribution to the drug was questionable.

From preclinical studies, it is thought that lower dose more frequent exposure schedules to inotuzumab may offer better anti-ALL efficacy. Following discussions in the Leukemia group and with Pfizer investigators, it was decided to study a different schedule of inotuzumab given weekly times 3. The total dose per course is the same, 1.8 mg/m^2. The treatment will be with inotuzumab 0.8 mg/m^2 on Day 1, 0.5 mg/m^2 on Day 8, and 0.5 mg/m^2 on Day 15. Courses are given every 3 weeks. When rituximab is required, it will be given weekly with inotuzumab. A total of 20 patients will be treated to gain experience with efficacy and toxicity. Early stopping rules will be implemented for an overall response rate < 40%.

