## **2.6 Update of December 2, 2011**

This study has completed accrual of 20 patients on the weekly schedule. The early analysis shows encouraging results with trends for similar or better efficacy and less

toxicity. Among the first 15 evaluable patients, 2 achieved CR (12%), 5 achieved CRp (31%) and 1 achieved CRi (6%). Thus, 8 of 15 evaluable patients (53%) achieved marrow CR. Five of the 7 evaluable responders (71%) achieved MRD negativity. Three patients underwent allogeneic SCT; no VODs were noted. Transient liver enzyme elevations grade 1-2 were noted in 5 of 20 (25%), severe in 2.

In discussions with Pfizer, we emphasized the importance of these findings but the limited number of patients makes definite conclusions difficult. It was agreed to increase the number of treated patients on the weekly schedule by another 20, for a total of 40 patients, to assess more precisely the response and toxicity profile compared with the 49 patients treated with the single dose every 3-4 weeks.

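### Section 10.0 keeps expected adverse events out of the CRF, so CRF-based toxicity rates would be too low on both schedules unless Appendix E says otherwise

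*Combined protocol and SAP*

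**What the plan says.** Section 10.0 restricts the form: "Only unexpected AEs will be recorded in the Case Report Form (CRF". The Principal Investigator signs the toxicity pages after each course, and the signed CRF then becomes the source for attribution. The section sends the reader to Appendix E for recording guidelines, and its serious-event part cites Appendix E again for data capture and source documents.

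The second objective in section 1.0 is "To evaluate the side effects of the treatment". Section 2.6 extends the weekly schedule to 40 patients "to assess more precisely the response and toxicity profile compared with the 49 patients treated with the single dose every 3-4 weeks". Section 11.3 repeats the aim of more precise response and toxicity rates. Section 11.2 makes the toxicity evaluation descriptive. Neither names a data source for toxicity.

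On which events count as expected, section 2.4 says: "Transient grade 1-3 elevations of liver enzymes have been observed, which are expected and self-limited". It also says: "Fever on Day 2 post therapy is common". The serious-event text in section 10.0 mentions expected events as already described, but the supplied text contains no list of them.

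**The concern.** The CRF is the natural source for a toxicity table. Here it is closed by rule to one class of event, and that class may include the toxicity the trial follows most closely. Liver events appear in all three updates, and section 5.3 makes the need for further cycles after the fourth depend on an assessment "based on response and liver toxicities with the previous 4 cycles".

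If the toxicity rates come from the CRF, they leave out non-serious expected events. Enrolling more patients narrows the interval around such a rate but does not remove the shortfall, so the stated reason for the extension would be only partly met. Attribution is the second stake. Section 2.5 reports that "Two patients had Grade 3 liver function abnormalities; the attribution to the drug was questionable", so in this trial the judgement needs to be made and recorded consistently.

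**Working it through.** **1. Where each kind of event is recorded, on the supplied text**

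| Event | CRF (section 10.0) | Other record |
|---|---|---|
| Unexpected | Yes, with the signed form as source for attribution | Section 7.0 examination before each subsequent course |
| Serious, expected or not | Only if unexpected | Serious-event route, from consent to 30 days after the last dose; hospitalizations to manage expected events go to the SAE log and annual report |
| Non-serious, expected, laboratory (e.g. liver enzymes, if so classed) | No | Section 7.0 chemistry: weekly in induction, then at least every 2 weeks; also the per-course examination |
| Non-serious, expected, non-laboratory (e.g. fever, if so classed) | No | Section 7.0 per-course examination |

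The section 7.0 record is not limited to unexpected events. It does not mention the CRF, a grade or attribution. Chemistry values allow a laboratory grade to be derived later, but not an attribution. What the last two rows lack is therefore a systematic CRF grade and attribution; other records of those events exist.

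**2. The plan's own figure**

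Section 2.6 reports: "Transient liver enzyme elevations grade 1-2 were noted in 5 of 20 (25%), severe in 2". The proportion reproduces: 5/20 = 0.25, exact (Clopper-Pearson) 95% interval 8.7% to 49.1%.

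**3. Direction of the error in a CRF-based rate**

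Let p be the true proportion of patients with the event and s the share of those patients whose event is classed as expected and so not entered. Then

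CRF rate = p × (1 − s), shortfall = p × s.

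The shortfall does not depend on the number of patients. With p = 0.25:

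- s = 0: 0.25 × 1 = 25%
- s = 0.5: 0.25 × 0.5 = 12.5%
- s = 1: 0.25 × 0 = 0%, i.e. 0/20 (exact 95% interval 0% to 16.8%)

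The documents give no value for s. These lines span its whole possible range to show the direction; they do not estimate an undercount.

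**4. Effect on the comparison of schedules**

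With W for weekly and S for single dose, the error in the CRF-based difference (W minus S) is

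[p_W(1 − s_W) − p_S(1 − s_S)] − [p_W − p_S] = p_S·s_S − p_W·s_W.

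Its sign depends on four unknown quantities. If s is the same on both schedules, the difference is multiplied by (1 − s) and so shrinks towards zero. If s differs, the error can go either way.

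**The case against.** The strongest reply is that the plan may already deal with this. Appendix E is cited for exactly this subject, is not among the supplied documents, and cannot be counted as missing. It may list the expected events and say where they are recorded. That stands, and it is why the point is conditional. Even so, section 10.0 states its restriction without exception, so if Appendix E differs the two need aligning.

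A second reply is that the data evidently exist. Section 7.0 has adverse events recorded before each course, serious events have their own route, and sections 2.4 to 2.6 report graded liver events and Day 2 fever. Section 2.5 shows that attribution was considered for two grade 3 liver cases. This also stands, and it limits the point to rates drawn from the CRF. A reader might infer that expected toxicity goes unrecorded in this trial, or that the rates in the updates are themselves too low. The documents support neither.

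Third, section 2.4 uses the word expected in a narrative and calls the fever common, which is not a formal classification. That is fair: whether these events fall under the rule is likely for the liver elevations and open for fever.

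**Conclusion.** The point holds in a limited form. Section 10.0 sets a recording rule that does not fit the side-effects objective or the purpose of the weekly extension. Toxicity rates taken from the CRF would be too low on each schedule where any non-serious event is treated as expected. This rests on two assumptions: that Appendix E does not modify the rule, and that the CRF is the source of the rates, which section 11.0 neither says nor excludes.

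The size cannot be estimated from the documents, and the direction of any effect on the comparison is unknown. A reader might be tempted to gauge the damage from the four severe liver cases, two in section 2.5 and two in section 2.6, by varying which are called drug-related. Those cases were captured and reported, so that exercise would show small numbers and uncertain attribution, not the effect of the CRF rule.

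The primary endpoint and the futility rules are unaffected.

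**What to change.** **Section 10.0.** Record in the CRF, whether expected or not, at least all grade 3 or higher adverse events and all hepatic adverse events, each with CTCAE grade and attribution. Sections 5.3 and 9.2 already require grade 3 or higher non-hematologic toxicity to be judged, and section 5.3 does so for liver toxicity. State that other non-serious expected events, such as fever, are taken from the per-course adverse event record in section 7.0. Reconcile both statements with Appendix E.

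**Section 11.0.** Name one common source for toxicity rates on both schedules. For patients already treated, use chart and chemistry records.

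**Cost.** Modestly more data entry, much of it for grades already judged during treatment; no new visits or procedures. Attribution may stay incomplete for past patients, because chemistry cannot supply it and the chart may not hold it. The report should say so.
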